6.1.2 Selection of Principal Investigators

All principal investigators will be required to demonstrate relevant experience and commitment. All investigators must have the particular medical expertise necessary to conduct the study in accordance to the protocol. Written agreement to conduct research as such will be obtained prior to site initiation.

The study intends to engage with the British Neurosurgical Trainees Research Collaborative (BNTRC) to appoint a trainee PI within each neurosurgery centre and the model for this has already been successfully established for trauma (RESCUE-ASDH) and hydrocephalus (BASICS) randomised controlled trials.

Hence the principal investigator at each site can constitute:

- Consultant level clinicians
- Trainee level clinicians

A suitable co-investigator should be identified at each site to deputise in case of PI absence.

IRAS ID: 287714 Page **25** of **53**

7. Eligibility Criteria

The PRIMROSE Tissue Study aims to recruit 300 patients. All patients must provide written, informed consent before any study procedures occur and must meet all eligibility criteria as described below.

7.1 Inclusion Criteria

Patients eligible for the trial must comply with all the following at enrolment:

- 1. Male or female.
- 2. ≥16 years of age
- 3. Histologically and/or cytologically confirmed breast cancer with CNS involvement, as defined as having one or more of the following:
 - a) Metastases to the brain parenchyma
 - b) Metastases to the leptomeninges
 - c) Paraneoplastic Neurological Disorders
- 4. FFPE of biopsied or resected primary breast cancer, non-CNS metastasis and/ or brain metastasis is available or will be available.
- 5. Informed consent

7.2 Exclusion Criteria

Any patient meeting any of the criteria listed below at baseline will be excluded from study participation:

1. Unable to comply with study procedures or give informed consent

7.3 Co-enrolment Guidelines

Participants can be recruited into other trials during their participation in this study. This will be documented as part of the follow up process. Individuals who have participated in any other studies or trials of any medicinal product can also be enrolled onto this study if eligible.

IRAS ID: 287714 Page **26** of **53**

8. Outcomes

8.1 Outcomes

Outcome	Outcome measures		
To investigate the concordance	Comparison of the following receptors in		
between the primary and brain	different tissue:		
metastasis for ER, PgR and HER2	Expression of ER, PgR and HER2		
The prevalence and concordance	Comparison of the following receptors in		
of the expression of the androgen	different tissue:		
receptor within brain metastasis as	Expression of androgen receptor		
compared to primary disease.			
To investigate the genomic	Measure the amount of cell free DNA		
landscape of CNS disease	within CSF		
secondary to breast cancer within			
CSF			

IRAS ID: 287714 Page **27** of **53**

9. Participant Timelines and Assessments

8.1 Participant Identification

Patients will be identified by the oncologist, neurologist, neuro-oncologist or clinical staff in direct care of the patient. Prior to a site being greenlighted, the necessary research team members will be made aware of the inclusion criteria of the study.

8.3 Informed Consent

Informed consent is a process initiated prior to an individual agreeing to participate in the study and continues throughout the individual's participation.

Informed consent is required for all patients participating in this study. In obtaining and documenting informed consent the investigator should adhere to GCP and to the ethical principles that have their origin in the Declaration of Helsinki.

Discussion and explanation of the study, using the Patient Information Sheet should be provided to patients by staff with appropriate experience. An appropriate Patient Information Sheet and Consent Form, describing in detail the study procedures and risks will be approved by an ethics committee and the patient will be asked to read and review the document. Upon reviewing the document, the investigator will explain the research study to the patient and answer any queries that arise. A contact point where further information about the study may be obtained will be provided to the patient. If a potential participant does want to withdraw from the study, they do not have to give a reason.

Permission will be sought, and all patients will be required to give informed consent prior to any study procedures.

Patients will be provided with the relevant Patient information Sheet and Consent form (PISC) detailing the study. Patients will be given the opportunity to read through and have an initial discussion of the study. Patients will be approached during their first or second clinic visit/appointment. Patients will be given a verbal introduction to the study by a member of the clinical research team with knowledge of the study. The patient will be provided with the relevant Patient information Sheet and Consent Form detailing the study. The patient will be given the opportunity to read through and have an initial discussion of the study. Patient will be given time to consider the study, and if they wish to take part will be asked to sign the relevant consent form.

IRAS ID: 287714 Page **28** of **53**

Consent will be obtained to take part in the study and to collect the following samples:

- Collection of Formalin Fixed Paraffin Embedded (FFPE) samples of primary breast cancer (from diagnostic biopsies), non-CNS metastasis (from diagnostic biopsies of brain metastases – where available) and brain metastasis (where available)

Informed consent should be re-affirmed throughout the study and all discussions and consent should be documented appropriately. The original signed document will be retained in the trial site's Investigator Site File (ISF) and copies will be made:

- One copy provided to the patient for their information,
- One copy transferred to the CTC via portal upload or encrypted email
- One copy filed in the participant's medical records paper/electronic.

N.B. Details of the consent process (date, persons involved, version and type of information sheet and consent form used) must also be recorded directly into the participant's medical records.

IRAS ID: 287714 Page **29** of **53**

9.3 Eligibility Assessment and Confirmation

Eligibility should be confirmed by an appropriately qualified member of the research team who is named on the delegation log. This must not occur until informed consent is documented. Eligibility Criteria are described in detail in Section 7.

Eligibility confirmation must be documented in the participant's medical notes and then on the relevant study CRF.

9.4 Screening and Registration Process

Potential study participants will be identified from patients who meet the inclusion criteria.

Patients will be provided with a patient information sheet and the accompanied informed consent form during clinic visits or by post/email following appropriate discussion with a member of the research team. The clinical research team will be available in person or by phone to discuss information relating to the study to interested patients.

After sufficient time for review and consideration of the study, patients will return to the clinic to address any questions and will be asked to provide informed written consent. Please note that in exceptional circumstances (i.e. when a patient lives far away from site or when the patient shows full understanding of the study and is agreeable to take part in the study) consent may be taken within the first visit.

Patients who meet the eligibility criteria outlined in section 7 and successfully fulfil the screening visit requirement will be enrolled into the study. The patient's GP and referring consultant will be informed of patient's decision to participate in the study according to consent provided by the study participants.

After a patient has been screened and their details MUST be entered onto eCRF database by the clinical study staff to register the patient and generate a Study ID for patient.

Participants will be registered via a secure (24-hour) web-based eCRF system controlled centrally by the LCTC. A personal login username and password, provided by the LCTC, will be required to access the registration system. Designated research staff will be issued with their personal login and password upon completion of training in the use of the system. This

IRAS ID: 287714 Page **30** of **53**

training will be coordinated by the LCTC. A Work Instruction will also be provided to sites to support the registration process.

When the system requirements (i.e. consent, eligibility) are confirmed the participant registration and a unique study number will be displayed on a secure webpage. An automated email confirmation will be sent to the authorised Principal Investigator and PRIMROSE Tissue Study team.

PRIMROSE Tissue Study Registration Details:

Web access: https://www.lcturedcap.org.uk/redcap/

[contact]

Email: [contact]

(Note that LCTC is open between 0900-1700, Monday – Friday, excluding public holidays)

In the event of a registration system failure, the centre should contact the coordinating team at the LCTC (Monday to Friday between 9:00 to 17:00 excluding Bank holidays) to try to resolve the problem. If the problem cannot be resolved the coordinating LCTC will perform central registration and provide the details over the phone.

To enable monitoring of the consent process and registration of patient, the following study documents should be forwarded to the LCTC by the Investigator/research site team within 2 days of a patient registration:

A copy of the Signed Consent Form signed by both the patient and the investigator

The documents should be uploaded to the PORTAL/emailed to the LCTC on Monday - Friday from 09:00 to 17:00 GMT, email: [contact]. Prior to sending documents, site staff should [contact] to inform the LCTC staff of the incoming documents.

9.3 Schedule for Assessments and Follow-up

Once consent has been obtained and documented and eligibility reviewed, the patient will be scheduled in for CSF collection as per their standard care pathway. This will be taken either by a lumbar puncture (with atraumatic needles) or aspiration of CSF from Ommaya Reservoir procedure or at the time of neurosurgery.

IRAS ID: 287714 Page **31** of **53**

The schedule of assessments is outlined below. The following research data and samples will be collected from the patient:

Procedures	At Registration (1st or 2nd Visit)	CSF Extraction Visit	Imaging/ Scan Visit	Disease Progression Visit
Data Collection				
Demographic Information	Х			
Disease history and characteristics	Х			
Prior cancer therapy (top line)	Х			
Current anti-cancer treatment and concomitant medications	Х			X
Progression Details				Х
Scan Data only Collection (no images to be collected)				
Scan Data Collection (as per standard care – CT, MRI etc.)			Х	
Tissue and CSF Sample Collection				
Routinely collected/	Х			Х

IRAS ID: 287714 Page **32** of **53**

Diagnostic FFPE		
block		
i) Collection of		
Primary Breast		
Biopsy and/or		
ii) Collection of non-		
CNS		
recurrent/metastatic		
tissue and/or		
ii) Collection of CNS		
Biopsy		
At time of standard		
care CSF sample		
extraction		
- Excess CSF		
sample	X	
collection –		
10ml		
- EDTA Blood		
tube – 10ml		
tabo Tomi		

IRAS ID: 287714 Page **33** of **53**

10. Procedures for all patients

10.1 Screening and Enrolment

Screening and enrolment will be completed as detailed in Section 9.4.

10.2 Registration Visit

Following patient enrolment, the following forms should be completed on the database using existing medical records/patient notes:

- i. Demographic Information
- ii. Clinico-pathological information
- iii. Prior Cancer Therapy

The available diagnostic and routine FFPE blocks for the patient should be requested from pathology as soon as possible after the patient is enrolled. The sample information should be logged on the database and the sample sent to the GCP Laboratories using the sample kits provided.

10.3 CSF Extraction Visit

The following procedures will occur at this visit:

- Blood sample collection (1 x 10ml EDTA blood tube) this should be collected immediately before the CSF extraction procedure
- CSF extraction (1 x 10ml CSF tube and 1 x 3ml 5ml CSF tube) this should be
 carried out via Lumbar Puncture or Ommaya Reservoir aspiration or at standard care
 neurosurgery as per standard procedure (atraumatic needles should be used unless
 discussed with PI & CI). The CSF samples for the PRIMROSE Tissue study will be
 excess samples taken at the time of the standard care CSF extraction procedure.

10.4 Scan/Imaging Visit

If the patient is booked in for a routine scan as part of their standard care pathway (e.g. MRI/CT scan), the Scan/Imaging visit eCRF should be completed. (No images to be collected only related data as per eCRF).

IRAS ID: 287714 Page **34** of **53**

10.5 Disease Progression Visit

If patient comes in for routine visit and there are no changes in disease or treatment, then there is no requirement to provide follow-up data.

In the event of patient disease progression, treatment changes or in the event of death, the following forms should be completed on the database using existing medical records/patient medical notes:

- i. Disease progression
- ii. Treatment changes
- iii. Death data (cause and date)

10.6 Participant Discontinuation/Withdrawal

In consenting to the trial, participants agree to all trial activities including sample collection and data collection. Every effort should be made to facilitate the completion of these for every recruited participant. If it is not possible to complete these activities (or it is deemed inappropriate) the reasons why should be documented.

Patients may be withdrawn from the study for any of the following reasons:

- Patient withdraws consent.
- Contraindications to collection procedures.
- Death
- Clinician-led:
 - Any change in the patient's condition which results in a contraindication to collection procedures or causes the patient to fall under the exclusion criteria.
 - Any change in the patient's condition that justifies discontinuation of involvement in the clinician's opinion.

Data to be collected at the time of discontinuation includes date of discontinuation and reason for discontinuation.

If a patient wishes to withdraw, the value of existing samples should be explained, and permission sought to continue retaining and using these. Generally, samples will be retained unless it is specifically requested for them not to be. Upon withdrawal, the LCTC and TMG should be informed in via eCRF and no further samples or data should be collected.

IRAS ID: 287714 Page **35** of **53**

Permission will be sought to use all samples collected thus far in the case of withdrawal. However, patients have the right to request that any samples which have not yet already been used in research to be disposed of. If a patient explicitly states that this is their wish, then the this should be recorded onto eCRF.

In some cases, it will be impossible to destroy the samples without affecting other samples as they will have been irreversibly linked to others (such as in cases of tissue microarrays being produced or plasma samples being pooled). In these cases, the sample itself will not be destroyed; however, information linking the sample to any patient identifiers will be destroyed, deleted or censored as appropriate to eliminate the link and make the sample unidentifiable.

10.7 Patient Transfer

If a participant moves from the area, every effort should be made for the participant to be followed-up at another participating trial centre and for this trial centre to take over responsibility for the participant.

10.8 End of Study

The end of the study is defined to be the date on which data for all participants is frozen and data entry privileges are withdrawn from the study database. The study may be closed prematurely by the Trial Steering Committee.

Site and study closure activities will be centrally coordinated and conducted in accordance with LCTC processes regardless of whether the study closes as planned or prematurely. This includes activities such as:

- End of Trial Notification to REC
- Checking that all site data entered onto the study database, discrepancies raised, and satisfactory responses received
- Quality Control checks of the Investigator Site Files and Trial Master File as appropriate.

IRAS ID: 287714 Page **36** of **53**

11. Samples

All PRIMROSE Tissue samples should be collected, processed, stored and shipped according to the PRIMROSE Tissue Laboratory Manual.

Sample kits will be provided, and postage costs will be covered by the trial.

11.1 Formalin Fixed Paraffin Embedded (FFPE) Tissue Samples

The following FFPE blocks will be collected for patients enrolled on the PRIMROSE Tissue Study where these samples were taken as part of the patient's routine care (or are planned to be taken as part of the patient's routine care) – e.g. diagnostic biopsies:

- Primary breast tumour tissue
- Non-CNS metastasis tumour tissue (where available)
- Brain metastasis tumour tissue (where available)

These samples should be shipped to the GCP Laboratory according to the PRIMROSE Tissue Study Laboratory Manual.

11.2 Blood (EDTA) Samples

A blood sample (1 x 10 ml EDTA) will be taken at the CSF Extraction visit (immediately prior to the CSF Extraction Procedure).

This blood sample should be processed at each trial site, stored at -80°C and transferred in batches to the GCP Laboratory Facility.

11.3 Fresh CSF Sample

Cerebrospinal Fluid samples will be collected at the time of a patient's routine CSF extraction procedure. This will either be carried out via Lumbar Puncture or Ommaya Reservoir aspiration or at standard care neurosurgery as per standard procedure. The CSF samples for the PRIMROSE Tissue study will be an excess sample taken at the time of the standard care CSF extraction procedure.

The following samples will be collected for the PRIMROSE Tissue Study:

• 1 x 10ml CSF sample

IRAS ID: 287714 Page **37** of **53**

Samples will be processed, stored and transferred to the GCP Laboratory Facility as per the PRIMROSE Tissue Study Laboratory Manual.

IRAS ID: 287714 Page **38** of **53**

12. Safety Reporting

Adverse events/safety events experienced by patients will not be recorded or reported for this study as all patients are receiving standard treatment decided by their clinical team and their care will not be influenced by the patient taking part in the PRIMROSE Tissue Study.

IRAS ID: 287714 Page **39** of **53**

13. Data Management and Study Monitoring

For the PRIMROSE Tissue study, the responsibilities for Data Management and monitoring are delegated to LCTC. Separate Data Management and Trial Monitoring Plans have been developed which provide detail regarding the internal processes that will be conducted at the LCTC throughout the trial. Justification for the level of monitoring is provided within these documents and the trial-specific risk assessment. All data will be managed as per local LCTC processes and in line with all relevant regulatory, ethical and legal obligations.

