- Site to send pathology request for sample collection
- Samples obtained from pathology by site research team and sent to GCP lab

Follow up

Until end of involvement in study (end of study, death or withdrawal):

- End of involvement entry created on eCRF
- · Final data entered into eCRF
- Database updated where applicable (e.g. in the case of withdrawal)

IRAS ID: 287714 Page **13** of **53**

4. Roles and Responsibilities

Sponsor

The Sponsor is the University of Liverpool and is legally responsible for the study. They will formally delegate specific sponsoring roles to the Chief Investigator and Clinical Trials Unit.

Chief Investigator

[name] is the Chief Investigator for the study and is responsible for overall design and conduct of the study in collaboration with other members of the study team.

Principal Investigators

In each participating centre a principal investigator and co-investigators will be identified to be responsible for identification, recruitment, data collection and completion of CRFs, along with follow up of study patients and adherence to study protocol at site. They will also be responsible for safety reporting and processing any applicable safety information.

Clinical Trials Centre

The Liverpool Clinical Trials Centre at the University of Liverpool in collaboration with the Chief Investigator, will have overall management responsibility and will be responsible for study management activities including (but not limited to) study planning, budget administration, Trial Master File management, data management, statistical analysis and participating site coordination.

Funder

This study is funded by: Daiichi Sankyo Europe GmBH. Please note that the current funding provided allows for all relevant tissue collection, processing and storage at the GCP Laboratories facility. Further funding will be sought (before tissue collection is complete) to conduct analysis and meet the stated objectives in this protocol. Should funding not be secured, the collected tissue samples will be transferred to the LCTC (previously LCTU) Post-Trial Tissue Bank (REC reference: 18NW0621).

IRAS ID: 287714 Page **14** of **53**

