5.3 Risks and Benefits

5.3.1 Potential Risks

The study collects tissue and CSF samples acquired during the patients' routine care. No additional procedures above those undertaken as part of routine care will be undertaken and therefore there is no additional risk for the patients by participation. For patients undergoing diagnostic or therapeutic lumbar puncture consent to allow a 10ml blood sample and an extra 10ml CSF sample to be taken in addition to the routine sample CSF taken as part of the

IRAS ID: 287714 Page **21** of **53**

procedure. There are anticipated to be no additional risk to patients by the taking of this additional sample.

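### The reasons Section 12 gives for recording no adverse events do not cover the study's own blood draw and extra CSF sample, and Sections 5.3.1 and 4 do not fit with it

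*Protocol*

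**What the plan says.** Section 12 (Safety Reporting) bars adverse and safety events from being "recorded or reported for this study as all patients are receiving standard treatment decided by their clinical team and their care will not be influenced" through participation. It makes no exception.

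Section 5.3.1 (Potential Risks) begins: "No additional procedures above those undertaken as part of routine care will be undertaken and therefore there is no additional risk for the patients". The next sentence of that paragraph reads: "For patients undergoing diagnostic or therapeutic lumbar puncture consent to allow a 10ml blood sample and an extra 10ml CSF sample", the CSF being on top of the routine sample. The paragraph ends by anticipating no added risk from the additional sample.

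The collections are confirmed elsewhere. Section 11.2: "A blood sample (1 x 10 ml EDTA) will be taken at the CSF Extraction visit". Section 11.3: "The CSF samples for the PRIMROSE Tissue study will be an excess sample taken at the time of the standard care CSF extraction procedure", with a volume of 10 ml. The schedule under 9.3 (Schedule for Assessments and Follow-up) lists both, and 10.3 places the blood draw immediately before the CSF procedure. Sections 9.3, 10.3 and 11.3 allow CSF to be taken by lumbar puncture, from an Ommaya reservoir or at neurosurgery.

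Section 4 says of principal investigators: "They will also be responsible for safety reporting and processing any applicable safety information".

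**The concern.** An exemption from event recording is reasonable in an observational study when everything that happens to the patient is routine care. Section 12 argues from that position, but the study is not wholly of that kind. A patient who does not take part would have neither the research blood draw nor the extra CSF volume. The stated reasons therefore support not recording events of standard care. They do not support leaving out events related to the study's own sampling.

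At stake is whether such an event could reach the study data, the LCTC and the oversight committees. Section 4.1 gives the TSC the decision on continuation, so it should be able to hear of harm from research sampling. Section 5.3.1 also matters in its own right, because it is the protocol's statement of risk and its first sentence is not accurate.

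**Working it through.** No arithmetic tests this point, and the protocol gives no figure to reproduce. The check sets the sections side by side.

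**1. What is taken only for the study, per CSF visit**
- Blood: 1 x 10 ml EDTA (5.3.1, schedule in 9.3, 10.3, 11.2).
- CSF: 10 ml beyond the routine sample (5.3.1, schedule in 9.3, 11.3).
- Section 10.3 also lists a second CSF tube of 3 to 5 ml without saying whether it is routine or research. If it were research, study CSF would be 10 + 3 = 13 ml to 10 + 5 = 15 ml. The point does not depend on this.

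**2. Section 12's reasons against that sampling**
- Treatment is standard and chosen by the clinical team: true of treatment, but the research samples are not treatment.
- Care is not influenced by taking part: this speaks to clinical management. It does not address two collections made because the patient takes part.

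**3. Section 5.3.1 against itself**
- First sentence: nothing beyond routine care, therefore no added risk.
- Next sentence: a blood sample and extra CSF. The blood draw in particular is an added procedure, so the premise of the first sentence fails.
- Routes: 5.3.1 names lumbar puncture only, which is 1 of the 3 permitted.

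**4. Section 4 against Section 12**
- Section 4 assigns responsibility for safety reporting. The word meaning 'where relevant' qualifies the processing of safety information, not the reporting.
- Section 12 says no event is to be reported for the study.

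**5. Which events still have a route into the study**

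| Situation | Route |
|---|---|
| Death | 10.5: cause and date |
| Progression or treatment change | 10.5: eCRF forms |
| Collection could not be completed | 10.6: reasons documented |
| Discontinuation, including for a contraindication to collection | 10.6: date and reason |
| Protocol deviation or potential serious breach | 15.4 |
| Non-fatal event after a completed research collection, patient continues, disease and treatment unchanged | None defined |

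The last row follows from Section 12 together with 10.5, which says that if "there are no changes in disease or treatment, then there is no requirement to provide follow-up data". Section 15.4 deals with departures from protocol or GCP. An event after a correctly performed collection is neither.

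**The case against.** The strongest reply is that this is a matter of wording in a low-risk study. The CSF is drawn during a procedure the patient has anyway. Section 5.3.1 discloses both samples and states that no added risk is expected. Section 13.5 rates the study Type A, comparable to standard care. Hospital records are source documents under 13.1. The Monitoring Plan and risk assessment, which are not shown, may say more. In a single-arm study, nothing separates an effect of the extra CSF from an effect of the routine procedure.

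Most of this stands, and it lowers the weight. It does not remove the point. Section 12 does not rely on the Type A rating or on the closing statement of 5.3.1, and it bars recording for the study outright. A subordinate plan should not have to override the protocol. The attribution problem is real and limits what a fix can deliver.

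A reader might infer more than the protocol supports:
- *That the study captures no safety-relevant information.* Sections 10.5 and 10.6 show otherwise.
- *That Section 4's safety role has no content at all.* It also covers the processing of safety information, and 15.4.2 requires potential serious breaches to be reported at once. The two sections fit badly, and no more than that is shown.
- *That the needle instruction in 10.3* ("atraumatic needles should be used unless" discussed with the PI and CI) *shows participation altering care.* Sections 9.3 and 10.3 place collection within standard practice, and nothing shows that these needles depart from what sites already use.
- *That the loss can be expressed as an upper limit on an event rate.* The protocol does not say how many of the 300 patients will have a CSF procedure, and it has no safety objective for such a limit to serve.

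**Conclusion.** The point holds in a limited form. Section 12's rationale does not cover the 10 ml blood draw and 10 ml extra CSF, 5.3.1 contradicts itself and names one route of three, and Section 4 does not fit with Section 12. The practical gap is one class of event: non-fatal, related to a completed research collection, in a patient who continues with disease and treatment unchanged.

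The weight is minor. The study is Type A, no outcome or analysis depends on safety data, and hospital notes may hold such an event. The conclusion rests on the protocol text alone and assumes that the unseen Monitoring Plan and risk assessment do not set up a separate reporting route. The number of patients exposed cannot be stated from the protocol.

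**What to change.** - **Section 12:** limit the exemption to events of standard care. Have sites record on a short eCRF form any event they become aware of that the PI judges related to the research blood draw or the extra CSF volume. Have them report it to the LCTC for the TMG and TSC. Add no visit and no follow-up contact.
- **Section 5.3.1:** remove the claim that nothing is added to routine care. State that the blood draw and the extra CSF are study sampling, for lumbar puncture, Ommaya reservoir and neurosurgery alike.
- **Section 4:** align the principal investigators' safety-reporting duty with this narrower scope.

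The cost is one protocol amendment, one short form and a small burden on sites. Two limits should be accepted openly. Events that sites never hear of will still be missed, because nobody is asked to look for them. Attribution between the routine procedure and the extra CSF will rest on PI judgement.
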